- v. Over the counter oral analgesics such as ibuprofen, acetaminophen, or even narcotics may be taken for discomfort. Prescription pain meds such as acetaminophen with an opiate and/or a gabapentin modulator such as Lyrica may also be prescribed short term for patient comfort. Application of cold or ice packs may be recommended for improved comfort.

M. Punctal plugs can be placed at the surgeon's discretion if needed to improve the tear film.

Treating both eyes on the same day:

2 options:

1. Sequential epithelium preparation, sequential UVA light administration: Prepare epithelium in one eye, load the cornea with CXLO Corneal Strengthening Solution, then prepare the epithelium in the second eye prior to initiating the UV light source. While one eye is receiving UVA light therapy, the other eye is receiving the loading dose of topical CXLO solution.
2. Bilateral epithelium preparation, simultaneous UV light treatment: Prepare epithelium in both eyes, and initiate CXLO solution drops in both eyes. After 10-90 minutes of loading both eyes with riboflavin, the eyes will be checked with a slit lamp or slit beam check. UV light treatment in both eyes will then be performed.

Post-Procedure Treatment Regimen Details:

Topical corticosteroids and antibiotics as per standard surgeon regimen following other UV procedures such as PRK may be used. Topical nonsteroidal medications and dilute anesthetic drops may be used as needed for early postop discomfort, but should be discontinued by post-procedure day 6.

5.0 STUDY PROCEDURES

5.1 INFORMED CONSENT

Prior to recruitment of any subjects into the study, written approval of the protocol, and informed consent and assent forms, must be obtained from the Institutional Review Board (IRB) for each participating clinical site.

Informed consent and assent forms, the assent form being applicable to subjects less than 18 years old, must be obtained and documented in writing prior to the initiation of any study procedures. The subject (or the subject's legally authorized representative) and the minor (when applicable) must be allowed sufficient time to thoroughly read (or have explained) the respective consent/assent form, which will be written at a level that can be understood by someone with minimal education.

The Investigator or his/her designee should answer any questions that the subject/representative might have. If the adult subject/parent/guardian and the minor, when applicable, agree to participate in the study, i.e., provides informed consent and assent, the subject/representative must sign both copies of the informed consent/assent forms. The witness and the Investigator must also sign both copies of these forms. One copy of these forms will be given to the subject/representative. If applicable, it will be provided in a certified translation of the local language.

Subjects who provide informed consent (and assent, if applicable) and document this in writing will be screened for eligibility. Screened subjects will be recorded on site-specific screening logs and once they are determined as being eligible, they will be enrolled into the study.

5.2 ASSIGNMENT OF SUBJECT IDENTIFICATION

A subject identification number (ID) will be assigned at screening. This ID should be used on all study-related documents. To maintain confidentiality, the subject's name should not be recorded on any study document other than the informed consent form.

5.3 CONCOMITANT AND EXCLUDED THERAPIES

Concomitant medications are any prescription drugs used by a subject during the study, until conclusion of study participation (Month 6-9) or early termination. The CRF will record administration of these medications.

No other experimental or investigational treatments are allowed during this study, including ocular experimental and investigational treatments in either eye.

5.4 TIMING OF STUDY ASSESSMENTS

All procedures will be performed according to the following schedule unless otherwise specified. When assessments are scheduled, subjects will be instructed to remove contact lenses prior to screening – 2 weeks prior for rigid/gas permeable contact lenses and 3 days prior for soft or scleral lenses – unless subject has no suitable vision correction option.

Pre-Procedure:

Assessments:

- UCVA
- Manifest refraction
- CDVA
- Pentacam corneal tomography
- Pachymetry by ultrasound or other scanning device such as Pentacam
- Slit lamp examination
- Intraocular pressure (IOP)

- Dilated fundus exam (or documented dilated fundus exam by another provider within 1 year)
- Medial history
- Contact lens history
- History of previous eye surgeries

Optional Assessments:

- Quality of life and/or comfort survey questions such as VFQ-25.
- Optional assessments including corneal wavefront, optical coherence tomography (OCT), Brillouin microscopy, iTrace wavefront aberrometry/topography, Orbscan corneal topography, tomography, contrast sensitivity testing, or other non-invasive diagnostic tools that may be available to an investigator.
- Previous ophthalmic history such as:
 - Previous old eyeglass prescriptions & topographic maps may be requested and documented.
 - UCVA within the past 3 months (if evaluation was performed at the same clinic as that involved in this study);
 - CDVA within the past 3 months (if evaluation was performed at the same clinic as that involved in this study);
 - Manifest refraction within the past 3 months (if evaluation was performed at the same clinic as that involved in this study).

Day 1 Post-Procedure:

Assessments:

- UCVA
- Slit lamp examination

Optional Assessments:

- CDVA
- Manifest Refraction
- IOP
- Pachymetry
- Optional assessments including Pentacam corneal tomography, corneal wavefront, optical coherence tomography (OCT), Brillouin microscopy, iTrace wavefront aberrometry/topography, Orbscan corneal topography, tomography, contrast sensitivity testing, or other non-invasive diagnostic tools that may be available to an investigator.

Optional Visit Days 2-10 (If Post-Procedure Day 1 shows incomplete epithelium healing):

Assessments:

- UCVA
- Slit lamp exam
- IOP

Optional Assessments:

- Manifest refraction and CDVA
- Pachymetry
- Optional assessments including Pentacam corneal tomography, corneal wavefront, optical coherence tomography (OCT), Brillouin microscopy, iTrace wavefront aberrometry/topography, Orbscan corneal topography, tomography, contrast sensitivity testing, or other non-invasive diagnostic tools that may be available to an investigator.

Interim visits may also be suggested in which similar safe non-invasive measurements may be obtained. Manifest refraction and non-contact corneal biomechanical and/or non-invasive biometry measurements may be obtained. These non-invasive measurements can be performed as frequently as the surgeon believes would be useful, especially in circumstances where the patient's vision and refraction can be expected to be changing rapidly.

Optional 1-2 month visit:

Some patients may experience significant changes in their refractive error, and may benefit from an optional visit at 1-2 months to get a new prescription for glasses or contact lenses.

Assessments:

- UCVA
- Slit lamp exam
- Pachymetry (ultrasound and/or Pentacam)
- Pentacam corneal tomography
- IOP

Optional Assessments:

- Optional assessments including corneal wavefront, optical coherence tomography (OCT), Brillouin microscopy, iTrace wavefront aberrometry/topography, Orbscan corneal topography, tomography, contrast sensitivity testing, or other non-invasive diagnostic tools that may be available to an investigator.
- Manifest refraction
- CDVA
- Medical and contact lens history will be recorded

Month 3 (60-120 days):

Assessments:

- UCVA
- Manifest refraction with CDVA
- Slit lamp exam (including rating of corneal haze if present from 0 (none) to 4)
- Pachymetry (ultrasound and/or Pentacam)
- Pentacam corneal tomography
- Medical and contact lens history will be recorded.
- IOP will be measured.

Optional Assessments:

- Quality of life and/or comfort survey questions.
- Optional assessments including corneal wavefront, optical coherence tomography (OCT), Brillouin microscopy, iTrace wavefront aberrometry/topography, Orbscan corneal topography, tomography, contrast sensitivity testing, or other non-invasive diagnostic tools that may be available to an investigator.

Month 6 (150-210 days):

Assessments:

- UCVA
- Manifest refraction with CDVA
- Slit lamp exam (including rating of corneal haze if present from 0 (none) to 4)
- Pachymetry (ultrasound and/or Pentacam)
- Pentacam corneal tomography
- Medical and contact lens history will be recorded.
- IOP will be measured.

Optional Assessments:

- Quality of life and/or comfort survey questions.
- Optional assessments including corneal wavefront, optical coherence tomography (OCT), Brillouin microscopy, iTrace wavefront aberrometry/topography, Orbscan corneal topography, tomography, contrast sensitivity testing, or other non-invasive diagnostic tools that may be available to an investigator.

Optional 1, 2, and 3 Year Post-Procedure Visits:

Patients may elect to return for 1, 2, and 3 year post-procedure visits as well as interim visits as per surgeon judgment.

Assessments:

- UCVA
- Manifest refraction with CDVA
- Slit lamp examination (including rating of corneal haze if present from 0 (none) to 4)
- Pachymetry (ultrasound and/or Pentacam)
- Pentacam corneal tomography
- Medical and contact lens history will be recorded.
- IOP will be measured.

Optional Assessments:

- Patient may be asked to answer quality of life and/or comfort survey questions.
- Optional assessments including corneal wavefront, optical coherence tomography (OCT), Brillouin microscopy, iTrace wavefront aberrometry/topography, Orbscan corneal topography, tomography, contrast sensitivity testing, or other non-invasive diagnostic tools that may be available to an investigator.

Option for additional simultaneous or sequential treatments:

- Patients may undergo a repeat CXL procedure following their 6-month visit. Patients will exit the study on that visit, and then will be re-enrolled as a new patient, and must meet all of the inclusion and exclusion criteria, and investigators must follow the same protocol as outlined above.

Unscheduled Visits

Interim visits may also be suggested in which similar, safe, non-invasive measurements may be obtained. Manifest refraction and non-contact corneal biomechanical and/or non-invasive biometry measurements may be obtained. These non-invasive, measurements can be performed as frequently as the surgeon feels would be useful, especially in circumstances where the patient's vision and refraction can be expected to be changing rapidly. Only unscheduled visits related to adverse event follow up will be recorded in the CRFs.

The timing of each scheduled assessment is summarized in Appendix 2.

5.5 WITHDRAWAL CRITERIA

Subjects have the right to withdraw from the study at any time, for any reason, without jeopardizing their medical care.

5.6 FOLLOW UP OF WITHDRAWN OR TERMINATED SUBJECTS

Subjects who withdraw from the study will be followed for safety where possible and encouraged to return for follow-up visits for any unresolved safety events.

Subjects who withdraw from the study will be asked to complete procedures outlined in the 6-9 month visit (if withdrawn prior to that visit). Subjects who are terminated due to adverse events will be followed, if possible, at least until resolution or stabilization of the adverse event.

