6.3 ANTICIPATED ADVERSE EVENTS

Epithelial Defect – A breach in the corneal epithelium that does not heal within 24 hours.

Persistent Epithelial Defect - A breach in the corneal epithelium that does not heal within 2 weeks.

Significant Decrease in Visual Acuity – loss of ≥ 2 lines CDVA

Sterile Infiltrates – Gray-white lesions caused by acute immune response to corneal damage.

Central Stromal Scars – New, significant corneal opacity in the central stromal region.

Corneal Haze – Cloudy or opaque appearance of the cornea. Grade Scale: 0 = clear cornea; 1 = focal areas of minimal stromal clouding or reticulation; 2 = diffuse mild stromal clouding or reticulation; 3 = Diffuse stromal clouding or reticulation somewhat obscuring the iris details; 4 = focal or diffuse areas of dense stromal haze obscuring iris detail.

Infectious Keratitis – Microbial infection of the epithelium or stroma.

Corneal Melt – A progressive, rapidly expanding, erosive, non-infectious, corneal ulcer.

Non-Infectious Keratitis – Inflammation of the cornea not associated with an infection.

Eye Pain – Eye pain lasting for >5 days.

Conjunctiva Hyperemia – Eye redness.

Foreign Body Sensation – Patient reports a feeling of a foreign body (e.g. gravel or sand) in the eye lasting >24 hours.

Corneal Hydrops – Acute corneal edema caused by a break in Descement membrane.

Herpes Simplex Virus (HSV) Reactivation – Epithelial keratitis, stromal keratitis, or disciform edema proven or clinically diagnoses as being caused by HSV.

Disease progression – Increase of $\geq 4D K_{max}$ as assessed by topography or tomography or loss of > 2 lines of CDVA.

Photophobia – Sensitivity to light lasting > 24 hours.

Elevated Intraocular Pressure (IOP) – IOP ≥ 30 mmHg or an increase in IOP of ≥ 10 mm from baseline recorded on two separate occasions or an increase in IOP that requires intervention.

Dry Eye Syndrome (DES) – Irritation of corneal surface due to inadequate production of tears that is consistently worse than the patient's pre-procedure state longer than 3 months after the cross-linking procedure.

Endophthalmitis – Diffuse intraocular inflammation predominantly involving the vitreous cavity but also involving the anterior chamber, implying a suspected underlying infectious cause.

Iritis – Presence of inflammatory cells in the anterior chamber. The presence of aqueous flare alone is not considered to constitute iritis.

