8.1 EFFICACY ENDPOINTS

The primary efficacy endpoint of this trial is change in corrected distance visual acuity (CDVA) at the last required study visit (6 months post-op), compared to baseline. CDVA will be evaluated by an observer who is masked to the treatment protocol to which study subjects have been assigned. All eyes treated (single or both eyes of an individual subject) will be included in the analysis of efficacy.

The Secondary Endpoints will be:

1. Change in UCVA at 6 months, compared to baseline.
2. Change in K_{\max} , compared to baseline.

Additional analyses will be performed in subgroups of patients using standard statistical stratification methods, including patients over the age of 35, patients under the age of 18, disease severity, and patients with and without pre-procedure corneal scars. Results in male vs. female patients and post LASIK ectasia vs. primary keratoconus will also be evaluated.

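### Protocol 5.6 does not ask subjects terminated for an adverse event for the Month 6 examination, so these eyes can lack the primary endpoint for reasons related to outcome

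*Protocol*

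**What the plan says.** Protocol 5.6 covers two classes of subject who leave early.

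- Those who withdraw: "Subjects who withdraw from the study will be followed for safety where possible", and "Subjects who withdraw from the study will be asked to complete procedures outlined in the 6-9 month visit (if withdrawn prior to that visit".
- Those terminated for an adverse event: "Subjects who are terminated due to adverse events will be followed, if possible, at least until resolution or stabilization of the adverse event". No visit and no acuity measurement is named for them.

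Neither class is defined. Protocol 5.5 deals only with the subject's own decision: "Subjects have the right to withdraw from the study at any time, for any reason, without jeopardizing their medical care". No section gives grounds for terminating a subject.

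The protocol's primary endpoint is "change in corrected distance visual acuity (CDVA) at the last required study visit (6 months post-op), compared to baseline" (8.1), and the same section adds: "All eyes treated (single or both eyes of an individual subject) will be included in the analysis of efficacy". The anticipated adverse events in 6.3 include "loss of ≥ 2 lines CDVA", central stromal scars, haze, infectious keratitis and corneal melt.

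The SAP does not impute missing values (3.6). It uses only the Month 3, 6 and 12 nominal visits for efficacy and leaves unscheduled visits out (5). Its own primary timepoint for the interim analysis is Month 12, with Months 3 and 6 supportive (5.1).

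**The concern.** The examination that supplies the primary endpoint is requested in words from one class of early leavers and not from the other. The class left out is the one defined by an adverse event, and several of the listed events bear directly on corrected acuity.

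The treatment is a single session, and a repeat procedure means exit and re-enrolment (Protocol 5.4). Once the procedure is finished there is no study treatment left to stop, so termination mainly ends the collection of outcomes.

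If these eyes do worse than the rest, their absence makes an arm's mean change look better than it is. If one irradiance or dose group has more such terminations than another, the comparison between groups shifts as well. The trial compares three UVA settings, and its data are meant to inform a Phase 3 design (SAP 1), so outcomes after complications matter.

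**Working it through.** The documents give no rate of termination for adverse events and no expected acuity deficit, so there is no figure to reproduce. The check has two parts: whether the gap follows from the text, and how large its effect could be.

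**Does the gap follow from the text?**

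1. Protocol 5.6 sets a minimum for terminated subjects that ends with the event. The minimum can be met before the Month 6 window opens at day 150.
2. Acuity measured while following the event is recorded, because unscheduled adverse-event visits go into the CRF (Protocol 5.4). SAP 5 keeps such visits out of the efficacy analysis, so that value cannot stand in for Month 6.
3. SAP 3.6 imputes nothing, so the eye drops out of that timepoint.
4. SAP 3.6 also states that the efficacy set has no missing primary data by construction. SAP 3.2.3 requires a change from baseline in only one of three endpoints, so a subject can be in the set without a Month 6 or Month 12 CDVA. The SAP therefore does not recognise this missingness.
5. The request to subjects who withdraw is itself unclear. It names a 6-9 month visit, while the schedule has a Month 6 visit with a window of 150-210 days in 5.4 and 150-180 days in Appendix 2. It does not say whether the procedures are done on leaving or at the scheduled time. SAP 3.8.3 assigns visits by nominal CRF visit, so an early exit examination entered on the Month 6 page could be analysed as Month 6.

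**How large could the effect be?**

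Let d be the share of an arm's eyes terminated for an adverse event with no Month 6 CDVA. Let D be how much worse, in logMAR, their mean change would be than that of the remaining eyes. If the observed mean is m, the full mean is (1 − d) × m + d × (m + D) = m + d × D. The observed mean is therefore too favourable by d × D. Both inputs are assumptions.

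| d | D = 0.2 | D = 0.4 |
|---|---|---|
| 1% | 0.002 | 0.004 |
| 2% | 0.004 | 0.008 |
| 5% | 0.010 | 0.020 |

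Between two arms the shift is (d2 − d1) × D:

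- 1% against 2% with D = 0.2 gives 0.01 × 0.2 = 0.002.
- 1% against 5% with D = 0.4 gives 0.04 × 0.4 = 0.016.

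For scale, assume 3,000 / 3 = 1,000 eyes per arm (equal allocation, one eye each) and an SD of 0.15 to 0.20. The standard error of a difference is SD × √(2/1000), which is 0.0067 to 0.0089. The assumed shifts run from well below one standard error to about two (0.016 / 0.0067 = 2.4; 0.016 / 0.0089 = 1.8). The interim efficacy set will be smaller, so its standard errors will be larger.

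**The case against.** The strongest case on the other side has five parts.

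- **The rule is a floor.** A reader might infer that terminated subjects are followed only until the event settles and then lose their endpoint. The text does not say that. It sets a minimum and does not bar a Month 6 examination. This stands: the supportable claim is that the examination is not requested, so the value can be missing.
- **The class may be small or empty.** A reader might picture a subject with early keratitis being removed once it stabilises. No section makes keratitis or any other event a ground for termination. By default such a subject stays in and has Month 3 and Month 6 CDVA, which are mandatory. A subject who chooses to leave because of an event has withdrawn and is already asked for the last-visit procedures. This also stands, and it limits the number affected. It does not remove the class, because 5.6 names it and gives it its own rule.
- **Safety information is largely kept.** A reader might infer that acuity after a complication is lost. Visual acuity loss is a safety assessment (Protocol 6.0), a loss of two or more lines is itself an anticipated adverse event, and serious cases are reported until the clinical outcome is ascertained (6.4). What can be missing is the scheduled, masked Month 6 measurement.
- **The mean effect is small and assumed.** At most 0.020 logMAR is a fifth of a line at 0.1 logMAR per line, and bias common to the arms cancels in comparisons. This stands as a limit on size.
- **The SAP is descriptive.** It tests no hypotheses (3.2.3.1), and its primary timepoint is Month 12. However, Month 6 is the protocol's primary endpoint and is still estimated. Month 12 is an optional visit that not every completer attends, so it does not reliably recover these eyes.

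**Conclusion.** The gap is real and modest. As written, a site can follow Protocol 5.6 in full without seeking a Month 6 CDVA from a subject terminated for an adverse event. The SAP has no means of replacing that value, although 8.1 puts all treated eyes in the efficacy analysis. Any such loss is likely to be related to outcome.

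The size is unknown. With 1-5% of an arm's eyes affected and a deficit of 0.2-0.4 logMAR, both assumed, the arm mean would be too favourable by 0.002-0.020 logMAR. The direction rests on these eyes doing worse than the rest, which is plausible from the events listed in 6.3 but is not shown. A reader might go further and conclude that every arm's mean is better than the truth, or that a harmful arm will look equal to a safer one. The documents do not support either, because they show neither how many subjects are terminated nor whether the rate differs by arm. The disposition table in SAP 4.1, which gives reasons for discontinuation, should at least show the number.

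One caution: the SAP cites protocol version 4.3, which is later than the protocol text reviewed here. Section 5.6 should be checked in that version.

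The change is worth making because it is cheap and does not touch care of the event.

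**What to change.** Replace the two follow-up rules in Protocol 5.6 with one, for example:

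*Unless they refuse further contact, subjects who withdraw or who are terminated because of an adverse event will be asked to attend the Month 3 and Month 6 assessments on schedule, including masked CDVA, UCVA and Kmax. This is in addition to follow-up of any adverse event.*

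Three further points:

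- Record the date of every such examination, so that an early exit examination is not filed as Month 6.
- Reconcile the 6-9 month visit in 5.6 (and the Month 6-9 end of participation in 5.3) with the Month 6 visit, whose window differs between 5.4 (150-210 days) and Appendix 2 (150-180 days).
- Leave exit for a repeat procedure (5.4) and the sponsor's right to terminate the study or an investigator (7.0) as they are. A rule that only withdrawn consent ends follow-up would conflict with both.

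The cost is a short protocol amendment and a few more visits, all of a kind already in Appendix 2. Reported mean gains may be slightly smaller. Management of the adverse event does not change.
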